- 1. Located in the Capital Region or Region Zealand in Denmark
- 2. Arrival of acutely admitted patients at the on-site Emergency department
- 3. Systemised use of Triage

Patient inclusion criteria

1. ≥18 years at contact to participating emergency department

Patients will be included at the first admission in the study period (index admission) and will remain in this group (intervention/control) for a follow-up period of 30 days.

All subsequent admissions (readmissions) will be ignored with regards to treatment group (i.e., you stay in the group you were first admitted into).

Exclusion

- Patients presenting in the ED with minor injuries (e.g. sprained ankle or minor cuts/abrasions) as they are triaged as blue (level 5) in both systems which typically precludes measurement of vital signs
- 2. Patient admitted directly to specialty ward (without contact to the emergency department)

Definition of clusters

Eligible hospitals can consist of one or two units. A hospital is defined based on its administrative organisation and catchment area. Each hospital will generate one cluster and two (time) periods (control and intervention). See schematic figure 1

Randomisation

Prior to the study start participating clusters will be randomised to start as either intervention or control. Eight clusters are available. The randomisation were performed using computer-generated numbers.

Ethics

The study was presented to the Regional Ethics Committee, who decided that no formal approval was needed in accordance with Danish law. Data management has been approved by the Danish Data Protection Agency (ID: P-2022-405).

Data:

The first 30 days after implementation of I-DEPT will be censored to minimize carry over effect. At follow-up (30 days after inclusion of last patient) the following data is collected from the National Patient Registry (NPR) and the electronic patient journal system Sundhedsplatformen:

- Contacts with the hospital system in the trial period.
- Information regarding admissions (date, time and place of admission and discharge, admission disrupted by patient).

- Information on vital signs and triage level
- Diagnoses (follow-up during study period, historical and in relation to index admission).
- Date of death or emigration (only very few cases of emigration are expected).

Outcomes:

Following outcomes are registered at clinicaltrials.gov (NCT04571021) on September 30, 2020

I-DEPT= Intervention

DEPT = Control

Primary outcome:

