Temperature, degrees Celsius			
Triage: Yellow, n (%)			р=Х
Female, n (%)			,
Age, years,			
Systolic Blood Pressure, mmHg			
Heart rate, pr. min			
Respiratory rate, pr. min			
Arterial oxygen saturation, %			
Temperature, degrees Celsius			
Triage: Green (least urgent), n (%)			p=X
Female, n (%)			
Age, years,			
Systolic Blood Pressure, mmHg			
Heart rate, pr. min			
Respiratory rate, pr. min			
Arterial oxygen saturation, %			
Temperature, degrees Celsius			
Missing triage			р=X

Table of summary statistics for patients for each group (intervention or control) will be presented for each triage of the four triage groups with baseline variables shown in Table 1.

Continuous variables will be summarized with mean and standard deviation or interquartile range (based on non-missing sample size).

Categorical variables will be reported as frequency and percentages (based on non-missing sample size) and number of missing values.

Categorical variables will be tested with chi-square.

Primary outcome analysis:

The primary outcomes will be an analysis of all-cause mortality within 30 days.

Patients will be followed as one cohort and data will be analysed as randomised and in accordance with the intention-to-treat principle.

- Patients (18+) will be included at the first admission at the participating hospitals in the study period (index admission) and will remain in this group (intervention/control) for follow-up of 30 days.
- Admission is defined as any contact to an emergency department where a Triage is performed
- Any patient lost to follow-up will be censored at the last time known to be alive.

Censored periods: Each period will start with 30 days of implementation, and the end of the study is followed by an observation period of 30 days. Periods of implementation and observation will be censored in the analyses (patients admitted in these periods will not be included in the analyses).

Main analysis

Logistic regression that accounts for clustering with adjustment for hospital ID, age, and sex, period (e.g., calendar month).

Results will be presented with distribution n (%) and Odds Ratio with a 95% Confidens interval and Risk difference with 95% Confidens interval. The assumption is that the actual intervention effect is 0. Non-inferiority will be assessed based on the risk difference with a non-inferiority margin (Δ) of 0.5%.

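### The primary model leaves out prior illness although historical diagnoses are collected; a score from pre-index diagnoses would cheaply remove some chance imbalance and variance

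*SAP*

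**What the plan says.** - **Model (SAP, Primary outcome analysis, Main analysis).** "Logistic regression that accounts for clustering with adjustment for hospital ID, age, and sex, period (e.g., calendar month"). Age and sex are the only patient-level covariates. The models for the secondary endpoints reuse this set, with question marks after period in several places.
- **Data (SAP, Data).** The list of register data includes "Diagnoses (follow-up during study period, historical and in relation to index admission"). The SAP does not say that any of these will be covariates.
- **Design (SAP, Definition of clusters; Randomisation).** "Each hospital will generate one cluster and two (time) periods (control and intervention"). "Eight clusters are available", and the order was assigned with computer-generated numbers.
- **Decision rule (SAP, Main analysis).** "Non-inferiority will be assessed based on the risk difference with a non-inferiority margin (Δ) of 0.5" per cent, alongside a 95% confidence interval.
- **Table 1.** It lists sex, age and vital signs within each triage colour. It has no comorbidity row and no block for all patients by arm.

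**The concern.** Only eight units are randomised, and patients arrive afterwards, so randomisation does little to balance case mix between DEPT and I-DEPT patients in this one trial. Prior illness would be expected to predict 30-day death and is fixed before triage, so it is a natural baseline covariate, and the data for it are already requested.

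The hospital and period terms deal with two sources of imbalance. They leave a third: a hospital whose patients become more or less comorbid over time, in a way other hospitals do not share and age and sex do not reflect. If such a change happens to line up with that hospital's switch, part of it enters the risk difference. The margin is only 0.5 points, so even small noise is worth removing. As Table 1 is laid out, readers could not judge the imbalance: it shows case mix only within triage colour, and colour is assigned by the system being compared.

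**Working it through.** The SAP gives no sample size, control mortality or comorbidity figure, so there is nothing of its own to reproduce. Everything below except the margin, the number of hospitals and the covariate list is an assumption, shown as a range.

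**Layout (assumed).** Eight hospitals over 19 months from September 2020. The switch months inferred from the dates in Figure 1 are Oct-20, Dec-20, Feb-21, Apr-21, Aug-21, Oct-21, Dec-21 and Feb-22. Each hospital's 30-day implementation month is dropped, leaving 8 × 19 − 8 = 144 hospital-months. The comorbid share in each hospital-month is regressed on treatment, and the treatment coefficient is the imbalance passed on to the comparison. Starting in November 2020 instead changes the results below very little.

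**Step 1. What hospital and period terms remove.** Let hospitals differ in comorbid share (SD 5 points) and let all hospitals drift together by 6 points over the study.
- Without the terms, the mean imbalance between arms is 2.2 points (SD 2.1).
- With hospital and separate-month terms, it is 0, to rounding error.

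The zero for common drift requires one term per separate month. The SAP offers calendar month only as an example, so a coarser coding would leave some common drift behind.

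**Step 2. What they leave.** Now let each hospital vary in its own way.
- Independent hospital-month variation, SD 1 to 3 points: the residual imbalance has SD 0.3 to 0.9 points.
- Autocorrelated drift (AR(1) coefficient 0.8 to 0.95, SD 1 to 2 points): SD 0.31 to 0.93 points.

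**Step 3. Effect on the risk difference.** Shift = (risk in comorbid − risk in others) × imbalance. Assume a gap of 6 to 9 points; 10% against 2.5%, for instance, is 7.5.
- Low end: 0.06 × 0.3 = 0.018, about 0.02 points; 0.02 / 0.5 = 4% of the margin.
- High end: 0.09 × 0.9 = 0.081, about 0.08 points; 0.08 / 0.5 = 16% of the margin.

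These are one-SD shifts, in either direction.

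**Step 4. Imbalance needed to use the whole margin.** Needed imbalance = 0.005 / (p1 − p0), where p0 is the risk without comorbidity and p1 follows from the odds ratio.
- p0 = 5%, OR 3: p1 − p0 = 0.0864, so 0.005 / 0.0864 = 5.8 points.
- p0 = 2%, OR 2: p1 − p0 = 0.0192, so 0.005 / 0.0192 = 26 points.

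Both are far outside the 0.3 to 0.9 range of step 2.

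**Step 5. Gain in precision.** At 4% mortality and 87,500 to 350,000 patients, the sampling standard error is 0.24 to 0.12 points. If the score removed all the drift, the interval would shorten by 1 − SE / √(SE² + drift²):

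| Sampling SE | Drift SD | Shortening |
|---|---|---|
| 0.24 | 0.02 | 0.3% |
| 0.12 | 0.02 | 1.4% |
| 0.24 | 0.08 | 5% |
| 0.12 | 0.08 | 17% |

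**The case against.** The strongest reply is that nothing here is an error. The covariate set is prespecified. Listing data to be collected does not promise their use as covariates, and the protocol, which is not at hand, may use the diagnoses elsewhere. Hospital and period are the terms that matter most in a stepped wedge, and both are in the model. The mortality gap is a crude one and is not net of age, which is already adjusted for, so even 4% to 16% may be generous. All of this stands. It makes the point an improvement, but does not remove the reason for it: the residual is real, the covariate precedes triage, and the data are already requested.

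A reader might infer three stronger things, none of which the document supports.

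- *That differences in prior illness pass uncorrected into the risk difference.* Step 1 shows that stable hospital differences, and common calendar changes under separate-month terms, are removed entirely.
- *That the estimate is systematically biased.* With randomised switch timing, hospital-specific drift unrelated to the order averages to zero over randomisations. It is mainly chance imbalance in the one order used. One could argue that counting only first contacts depletes frequent attenders over time, but separate-month terms also remove such depletion where it is uniform across hospitals.
- *That half the margin is at risk.* That needs a residual imbalance of about 3 points: 0.09 × 3 = 0.27 points, 54% of the margin. Against an SD of at most 0.93, this is at least 3.2 SD.

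**Conclusion.** The point holds as a modest improvement to the analysis. The primary model adjusts for hospital, period, age and sex and omits prior illness. What stays unadjusted is hospital-specific change in comorbidity over time beyond age and sex. Its likely size is smaller than the sampling error assumed in step 5, and the top of the precision range needs both the largest trial and the largest drift considered. The figures rest on switch dates inferred from Figure 1, on separate-month terms, and on assumed drift, mortality gap, overall mortality and patient numbers. None of these sizes is in the SAP, so they show the order of magnitude and do not predict the result.

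**What to change.** Before outcome data are seen:

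1. Add a comorbidity score (for example Charlson categories) to the primary model and to the secondary models that copy its adjustment. Build it only from diagnoses recorded before the index contact, and state the look-back window.
2. Exclude diagnoses made at the index admission or during follow-up. They come after triage and may be affected by it.
3. Keep the present model with hospital, period, age and sex as a named sensitivity analysis.
4. State that period is coded as separate calendar months across the study, since the removal of common drift depends on it.
5. Add an all-patients block by arm to Table 1, including the score.

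The cost is one derived variable from data already requested, some SAP wording, and a change to the prespecified covariate set, which should be dated and explained. No new data and no patient burden are involved. If outcome data have already been opened, the score-adjusted model should be reported only as a labelled sensitivity analysis.

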Official title of the study:

Implementation of the Individual Danish Emergency Process Triage (I-DEPT)

Statistical analysis plan

Original version: June 14, 2022, Latest revised version: January 24, 2023 Latest upload date/Document date: March 30, 2023

Clinical trials registration: NCT04571021

Principal Investigator (PI) [name]^{1,2}, M.D., D.M.Sc., Co-PI [name].

Chief Statisticians

[name], [name].

Contributors to analysis and interpretation of data

Statisticians, Primary Investigators and Steering Committee

This document contains the statistical analysis plan for the I-DEPT study. The statistical analysis plan has been completed prior to the availability of the outcome data and aims to clarify the analyses.

Short summary

Triage systems have been implemented in most emergency departments (ED) to minimize crowding and treatment delays that can result in adverse patient outcomes. Triage systems with limited room for clinical judgment are used by emergency departments (EDs) worldwide. The Individual Danish Emergency Process Triage (I-DEPT) is a new simplified triage system with a clinical assessment. I-DEPT is designed to simplify risk prediction and to reintroduce clinical judgment as the central part of triage. In this trial we compare I-DEPT with a traditional triage model in terms of risk prediction and patient outcomes, with a focus on 30-day mortality. Intervention: I-DEPT is a new triage system constructed from data collected from 12 000 ED patient visits at a large Danish hospital. I-DEPT solely consists of a quick score of vital signs followed by a basic clinical assessment by an ED nurse. The final triage level results from a score calculated after measurement of vital signs corresponding to a triage level of 1-4, that is then adjusted by the ED nurse, who can either up-triage (up to 2 steps) or down-triage (1 step) according to clinical assessment with no specific explanation needed. The development of the I-DEPT (former called Copenhagen Triage Algorithm, CTA) has previously been described in detail (1). I-DEPT has previously been compared to the Danish Emergency Process Triage (DEPT) which is a local adaption of Adaptive Process Triage. The two triage systems were compared in a noninferiority, two-center cluster-randomized crossover study, where I-DEPT was non-inferior to a traditional triage algorithm by short term mortality, and superior in predicting 30-day mortality (2).

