Control: DEPT; is a local adaption of the Adaptive Process Triage (ADAPT), triage model developed in Sweden in 2006 like most other well-known triage models, was the standard triage model used in the study. It includes the presenting (or chief) complaint in addition to a list of vital signs with cut-off values corresponding to each triage level. These are both registered, and the final triage level is determined by the most urgent triage level assigned Both triage systems identify five levels of urgency with colors (red, orange, yellow, green, and blue). The least urgent of these (the fifth level) was excluded from this study as it is defined as non-emergent patients (e.g. minor injuries) and includes no indication for measuring vital signs.

Aim of the study

The aim of the study is to investigate the impact of I-DEPT that has a systematic involvement of clinical assessment and the possibility to adjust the triage. I-DEPT will be compared to the existing DEPT with a focus on mortality, critical illness/distribution within risk groups and time to assessment

Hypothesis

The main hypothesis is that I-DEPT will be non-inferior to the existing DEPT regarding 30-day mortality.

Timeline

The study will start at October 1, 2020. Due to implementation patients will be enrolled from November 1, 2020 with planned end of inclusion, April 1, 2022. Follow-up will be concluded on May 1, 2022. The primary analysis will be conducted when the last patient has been followed for 30 days and data is available, which is expected to be November 2022.

Study design;

Hospital	1. sep-20	1. okt-20	1. dec-20	1. feb-21	6. april-21	1. juni-21	1. aug-21	1. okt-21	1. dec-21	1. feb-22	1. april-22
Nykøbing Falster Sygehus											
Herlev & Gentofte Hospital											
Sjællands Universitetshospital											
Bispebjerg & Frederiksberg Hospital											
Nordsjællands Hospital											
Slagelse Sygehus, Bomholms Hospital											
Hvidovre & Amager & Glostrup Hospital											
Holbæk Sygehus											
	Baseline										Follow-up
Censureringsperiode											
Studieperiode											
Follow-up periode, 30 dage											

Figure 1: Cluster-randomised step-wedged" design

Note: There was a break between implementation at Bispebjerg og Nordsjaelland

The reason for the break was organisational challenges due to summer holidays with lower staffing in that period.

Inclusion/Exclusion criteria

Eligible Emergency departments

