Cumulative incidence plots (1-survival) will be calculated using the Kaplan-Meier method and presented with Hazard Ratio and 95% Confidens interval and adjusted for the same variables as the main analysis.

Additional cox regression censoring for "Do not resuscitate order" will also be performed.

Sensitivity analyses of the primary endpoint:

In addition to the ITT analysis, a per-protocol analysis will be performed. In this analysis, interventional patients with missing or incomplete triage will be excluded.

Subgroup analyses of primary endpoint:

The primary outcomes will be calculated for the following subgroups, including a test for interactions.

Results will be presented with distribution n (%) and Odds Ratio with a 95% Confidens interval and illustrated in a Forrest plot and/or Cumulative incidence plots (1-survival) will be calculated using the Kaplan-Meier method.

Following subgroups are planned:

- Triage groups (green to red)
- Age (\leq 39 years, 40 to 69 years, \geq 70 years)
- Medical specialties
- Surgical specialties

Secondary endpoints:

Patients in the orange triage category (I-DEPT vs. DEPT) – including all-cause mortality within 30days:

Main analysis

Same as primary outcome:

Logistic regression that accounts for clustering with adjustment for hospital ID, age, and sex,

period

Results will be presented with distribution n(%) and Odds Ratio with a 95% Confidens interval

Doctor assessment (I-DEPT vs. DEPT)

Time from triage to arrival of a doctor

Main analysis

Distribution will be investigated with Boxplot

Cox regression following the same adjustment principles as for the primary outcome (age, sex, hospital id, period)

Results will be presented with Hazard ratio with a 95% Confidens interval

Length of stay (I-DEPT vs. DEPT)

- The total number of days admitted to a hospital within 30 days

Main analysis

Distribution will be investigated with Boxplot

Linear regression following the same adjustment principles as for the primary outcome (age, sex, hospital id, period?)

Results will be presented with mean days (SD or Interquarentile range) for both groups and difference in hours with a 95% Confidens interval

Time in the Emergency Department (I-DEPT vs. DEPT)

- Time spent in the Emergency department from triage to either admission, transfer or discharge

Main analysis

Linear regression following the same adjustment principles as for the primary outcome (age, sex, hospital id, period?)

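### The per-protocol analysis drops missing or incomplete triage from the I-DEPT arm only, so it can show a risk difference where none exists

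*SAP*

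**What the plan says.** The SAP section on sensitivity analyses of the primary endpoint adds a per-protocol analysis to the intention-to-treat analysis and gives one rule for it: "In this analysis, interventional patients with missing or incomplete triage will be excluded". The Outcomes section fixes the vocabulary with "I-DEPT= Intervention" and names DEPT as control. No other sentence removes DEPT patients on the same ground.

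Table 1 of the baseline description has an I-DEPT column, a DEPT column and a row labelled "Missing triage", so the plan provides for missing triage in both arms.

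The main analysis is a logistic regression that accounts for clustering and adjusts for hospital, age, sex and calendar period. On the decision, the SAP states: "Non-inferiority will be assessed based on the risk difference". The margin is 0.5%, and the true effect is assumed to be 0.

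**The concern.** Whether triage is completely recorded is settled after arrival and may be related to how ill the patient is. Very sick patients may be treated before scoring is finished, and very well patients may be scored in part or leave. Removing such patients from one arm changes the risk profile of that arm alone. The comparison is then between selected I-DEPT patients and unselected DEPT patients.

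The covariates contain no vital signs, severity or presenting complaint, so a difference in mortality between excluded and retained patients need not be adjusted away. The error can go either way. Excluding higher-risk patients makes I-DEPT look better, and excluding lower-risk patients makes it look worse.

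What is at stake is the reading of this one analysis. The SAP's other checks on the primary outcome are the repeats with 60 and 90 days of censoring after implementation and the Cox model that censors at a do-not-resuscitate order. Neither examines triage completeness. As written, agreement or disagreement between the per-protocol and intention-to-treat results could come from the one-sided filter.

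**Working it through.** The SAP has no figure to reproduce: it states no mortality, no rate of missing triage and no mortality for patients without complete triage. Only the 0.5-point margin and the assumed null effect come from the document. The other values below are assumptions.

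**Formula.** Let *p* be overall 30-day mortality, equal in both arms; *f* the share excluded; and *R* the mortality of excluded patients divided by that of completely triaged patients. If *c* is mortality among the completely triaged, then p = (1 - f)c + fRc, so c = p/(1 - f + fR). With I-DEPT filtered and DEPT not, the spurious risk difference (I-DEPT minus DEPT) is c - p.

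**One-arm rule, p = 3.5%.** For f = 5% and R = 3: 3.5%/(0.95 + 0.15) = 3.182%, and 3.182% - 3.5% = -0.318 points. Likewise:

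| Share excluded | R = 3 | R = 0.5 |
|---|---|---|
| 1% | -0.069 | +0.018 |
| 2% | -0.135 | +0.035 |
| 5% | -0.318 | +0.090 |
| 10% | -0.583 | +0.184 |

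The error equals the margin when 3.5%/(1 - f + fR) = 3.0%, that is f = 8.3% for R = 3 and f = 16.7% for R = 2.

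**What adjustment can do.** Suppose 30% of patients are older with 9% mortality and 70% younger with 1.143% (overall 3.5%), and that 12% and 2% of them are excluded (overall 5%).

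- If excluded patients have the same mortality as others of their age, crude R is 2.04 and the crude error is -0.174, but the error standardised to the 30/70 age mix is 0.000.
- If they have 1.5 times the mortality of completely triaged patients of the same age, the completely triaged have 9%/1.06 = 8.491% and 1.143%/1.01 = 1.132%. The standardised mortality is 0.3 × 8.491% + 0.7 × 1.132% = 3.339%, an error of -0.161. Crude R is 3.04 and the crude error -0.323.

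Adjustment therefore removes the part that the covariates explain and leaves the rest.

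**Simulation.** A layout with 8 hospitals, 16 periods and no true effect was analysed by logistic regression on hospital, period, age and sex. An unmeasured severity variable drove both missing triage and death. Mortality was 3.5% and 4.7% had missing triage; mortality was 6.4% in those and 3.4% in the others. Excluding from I-DEPT only gave -0.17 points (Monte Carlo SE 0.03). Excluding from both arms gave -0.01 (SE 0.04).

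**Two-arm rule, p = 3.5%, R = 3 in both arms.** The error is p/(1 - fI + fI·R) - p/(1 - fC + fC·R), with fI and fC the shares excluded from I-DEPT and DEPT.

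| I-DEPT excluded | DEPT excluded | Two-arm rule | One-arm rule |
|---|---|---|---|
| 5% | 5% | 0 | -0.318 |
| 5% | 3% | -0.120 | -0.318 |
| 5% | 8% | +0.165 | -0.318 |
| 2% | 8% | +0.348 | -0.135 |

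The two rules err equally when DEPT exclusion is 4.2% against 2% in I-DEPT, or 11.1% against 5%, so roughly when DEPT loses twice as many. Beyond that the two-arm rule is worse.

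**The case against.** The best case for the rule is that a per-protocol analysis asks whether the new system, used as intended, is safe, and that DEPT as existing practice needs no such filter. The SAP does not state that aim, and it would not cure the selection: an unfiltered comparator still holds the kind of patient removed from I-DEPT. DEPT is also a defined system whose triage can be incomplete: "It includes the presenting (or chief) complaint in addition to a list of vital signs".

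Second, the excluded group may be small, since "Admission is defined as any contact to an emergency department where a Triage is performed". This limits wholly missing triage and makes the higher rates in the table less likely. It does not limit incomplete triage, and the SAP does not say whether missing means performed but not recorded.

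Third, the SAP plans multiple imputation when more than 5% of a variable in a planned analysis is missing, and triage level is such a variable. Every rate at which the illustrated error reaches the margin lies above 5%. But that rule does not change whom the per-protocol analysis excludes, and the SAP does not connect the two.

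Fourth, the simulation has unmeasured severity built in. That is correct: it shows that adjustment fails when such a factor exists, not that one exists here.

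Fifth, the two-arm rule is not always better. This stands. Besides the unequal rates above, with 5% excluded in each arm, R = 1 in I-DEPT and R = 3 in DEPT, the current rule gives 0 and the two-arm rule +0.32. Reporting the excluded patients by arm is therefore part of the remedy.

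**Conclusion.** The concern holds. As worded, the per-protocol analysis conditions on triage completeness in one arm only, and the SAP gives no reason for this. Whether this biases the result depends on whether excluded patients differ in mortality beyond hospital, age, sex and period; neither the sign nor the size can be fixed from the SAP. Under the assumed 3.5% mortality the crude error is small with 1% to 2% excluded (at most 0.13 points for R from 0.5 to 3), about a third of a point with 5% excluded and R = 3, and reaches the margin only at 8.3% or more for R up to 3. Adjustment may remove some or all of it.

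The primary intention-to-treat analysis and the non-inferiority decision are not affected. The defect is secondary, but it sits in the only analysis listed under that sensitivity heading and is cheap to correct.

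**What to change.** Reword the rule along these lines: *Patients in either period whose triage under the system in force is missing or incomplete will be excluded.* State that the analysis uses the same adjusted model and the same risk difference as the main analysis.

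Once the rule covers both systems, say what counts as incomplete in each, because their components differ (for I-DEPT: "I-DEPT solely consists of a quick score of vital signs followed by a basic clinical assessment by an ED nurse"), and whether missing means performed but not recorded. A reference will do if the protocol already settles this.

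Report the number and 30-day mortality of excluded patients by arm. Table 1 already provides a row for missing triage; the mortality and the count of incomplete triage are new. Similar rates and mortality in the two arms would support reading the two-arm result at face value. Clearly different ones would signal remaining bias.

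The cost is a change of SAP wording and one small table. Some DEPT patients leave this sensitivity analysis, and the error could exceed the present one if DEPT exclusions are more than about twice those in I-DEPT. The intention-to-treat population, model and margin stay as they are.
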